In recent years, immune checkpoint inhibitors (ICIs) have become a new option for the treatment of bladder cancer. A study of 114 patients with MIBC(T2-4aN0M0) showed that a complete pathological response rate (CRR) of 37% was achieved with three courses of neoadjuvant immunotherapy with 200 mg Pembrolizumab before radical resection [3-4]. A one-arm second-stage clinical trial included 95 patients with MIBC who received two cycles of Atezolizumab before radical resection. About 31% of the patients experienced complete pathological reaction during radical resection. The pathological stage of more than half of the patients was reduced to NMIBC, and the one-year recurrence-free survival rate (RFS) was 79% [5]. The above studies have demonstrated that neoadjuvant immunotherapy based on ICIs is a therapeutic option for patients with MIBC, especially those who are intolerant to chemotherapy. Studies have confirmed that after tumor resection, neoadjuvant immunotherapy will continue to trigger a stronger immune response mainly by CD8+ T lymphocytes, leading to longer survival time for patients [6]. In addition, the surgical safety of radical resection after neoadjuvant immunotherapy is not significantly different from other methods [7]. Although ICIs can benefit more patients with MIBC than neoadjuvant chemotherapy, the use of ICIs still faces many challenges. First, there are currently no biomarkers that can predict the sensitivity of patients with MIBC to new ICIs-based adjuvant immunotherapy. The guidelines point out that PD- L1 expression and tumor mutation burden may predict the pathological response of ICIs treatment in some patients, but it is still not recommended as the basis of treatment selection [8]. Second, some patients lose the opportunity of radical surgery due to adverse events caused by ICIs treatment [9]. Finally, there is still controversy over whether ICIs alone or in combination with other immune and chemotherapy regimens is optimal.

A C014 study published on ASCO 2021 showed excellent anti-tumor activity with the combination of vidicon and tripril monoclonal antibody, with a therapeutic ORR of 94.1% in 17 evaluable patients. The ORR of the combination regimen was also 100% in 10 new patients. Further

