In this study, we intended to add immunotherapy to the treatment of patients with locally advanced urothelial carcinoma of the bladder who were intolerant to locally advanced cisplatin, so as to obtain the efficacy and safety indicators for the platinum-intolerant patients with locally advanced urothelial carcinoma of the bladder treated with the neoadjuvant therapy of vidicon combined with Ampley monoclonal antibody, and to provide guidance for the follow-up Phase III clinical trial and clinical application.

III. Study purpose and endpoint

1. Research purposes

1.1 Main research objectives:

To evaluate the pathological complete response rate (pCR rate) after radical cystectomy in patients with HER2 expression, cisplatin-intolerant cT2-T4aNxM0 vesical urothelial carcinoma treated with neoadjuvant therapy of vidicon combined with Ampley monoclonal antibody.

1.2 Secondary study objectives:

A) Evaluating the pathological descending rate;

B) Evaluating event-free survival (EFS);

C) Evaluating overall survival (OS);

D) To evaluate the safety of the new adjuvant therapy and its impact on radical cystectomy (evaluated according to NCI-CTCAE v5 and surgical complications according to Clavien-Dindo scoring criteria).

2. Analysis set:

2.1 Safety analysis set: Includes all patients who received at least 1 dose of any study drug (any component of neoadjuvant combination therapy).

2.2 Effectiveness analysis set: Includes all patients who received at least 1 dose of any study drug treatment (any component of neoadjuvant combination therapy) and had a radical cystectomy following that treatment.

3. Observation indicators

3.1 Main indicators:

Pathological complete response rate (pCR rate): the pathological stage after radical cystectomy was pT0N0 (based on effectiveness analysis)

3.2 Secondary indicators:

A) Pathological decline rate: the proportion of patients with pathological stage \leq pT1N0 (based on the efficacy analysis set) after radical cystectomy;

B) Safety: to evaluate the safety and impact on radical cystectomy of the new adjuvant therapy (evaluated according to NCI-CTCAE v5 and surgical complications according to Clavien-Dindo scoring criteria) (based on the safety analysis set);

C) Event-free survival (EFS): EFS is defined as the time from enrollment to disease progression, death from any cause, or new onset of another tumor.

D) Total survival (OS): Total survival was defined as the time from enrollment to death for any cause.

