3. The investigator judges that the operation timing is delayed, including but not limited to: disease progression occurs in the new adjuvant treatment stage or AE fails to complete 4 cycles of new adjuvant treatment, and the operation is not performed although it is assessed by the investigator to be in line with the indications for radical surgery;
4. Combined use of any anti-tumor therapy;
5. Patients fail to comply.

Patient withdrawal (individual patient ends the study): A patient may withdraw from the study for the following reasons, including but not limited to the following: 1. The patient withdraws informed consent; 2. Death; 3. Loss of follow-up.

V. research design

5.1 overall design

This is a multicenter, open-label, single-arm prospective clinical study to evaluate the efficacy and safety of neoadjuvant treatment with vidicon and Ampley monoclonal antibody in patients with cisplatin-intolerant cT2-T4aNxM0 urothelial carcinoma of the urinary bladder. In the absence of active withdrawal from the trial, intolerable drug-induced toxic and side effects, or findings that the subject was considered by the investigator to be unsuitable for further trials, each subject will undergo post-treatment surgery according to the following protocol, with efficacy evaluation and follow-up at each cycle.

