5.2.4 Surgical treatment

Preoperative evaluation will be performed prior to radical surgery, and if the patient meets the surgical indications, the investigator will perform radical cystectomy at an appropriate time as planned; If the patient is not suitable for surgery, the investigator decides to administer subsequent treatment. Disease progression occurs during the neoadjuvant treatment phase, or the AE fails to complete 4 cycles of neoadjuvant treatment (total neoadjuvant treatment duration does not exceed 15 weeks), but if the investigator assesses that the indication for radical surgery is met, surgery will be continued within the specified time frame and will still be considered eligible for treatment and evaluation for all study requirements. If the investigator determines that physical conditions preclude radical surgery, study treatment will be discontinued, an end-of-treatment visit will be given, and additional treatment selected by the investigator will be continued. If any of the conditions exceed the above time limits, but the investigator determines that the procedure is still acceptable, the team

leader unit will be contacted to determine whether or not they are eligible for study analysis. Patients who discontinue neoadjuvant therapy early due to disease progression or an intolerable adverse event (AE) before surgery and do not undergo surgery are given an end-of-treatment visit and will continue to receive other treatments selected by the investigator.

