5.3.4 Tumor and Efficacy Evaluation

5.3.4.1 baseline neoplastic imaging will be performed prior to enrollment with multiparameter magnetic resonance imaging of the bladder (or pelvis) (which must be reassessed post-TURBT if TURBT) and computed tomography (CT) scans of the chest, whole abdomen, and pelvis (enhancement to be determined by the investigator if necessary).

While 5.3.4.2 is on treatment, multiparameter magnetic resonance imaging of the bladder (or pelvis) will be performed (with a conditional VI-RADS score) and computed tomography (CT) scans of the chest, whole abdomen, and pelvis (enhancement at the discretion of the investigator if

necessary) prior to and prior to the start of cycle 3 of neoadjuvant therapy according to RECIST version 1.1:

1. Assessed prior to the start of cycle 3 and continued treatment as planned if the patient did not develop PD; • if the patient has PD, subsequent treatment at the discretion of the investigator;

2. Pre-operative evaluation. If the patient meets the operation indication, the researcher shall select appropriate time to perform radical cystectomy according to the plan; If the patient is not suitable for surgery, the investigator decides to give subsequent treatment;

3. After radical surgery, the pathological stages after neoadjuvant treatment will be evaluated by the researchers based on the pathological results of surgical samples.

4. Computed tomography (CT) scans of the chest, whole abdomen, and pelvis are performed 3 months, 6 months, 12 months, 18 months, and 24 months after the radical resection (enhancement is judged by the researcher if necessary). The former shall prevail until the disease progression, death, withdrawal of informed consent, loss of follow-up, conclusion of study follow-up or initiation of new anti-cancer treatment (surgery) of the patient occur.

The investigator will evaluate the response using RECIST 1.1.

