5.4 Statistical analysis

5.4.1 Sample size and calculation basis

The historical control pCR rate was assumed to be 10% based on recent clinical studies. The expected pCR estimate for this study was 25%, representing a clinically significant improvement. The resulting zero and alternative assumptions are as follows:

The original assumptions to be tested were: h_0 : PCR rate = 25%

Corresponding alternative hypothesis: h_a : pcr rate > 25%

The Simon Phase II (Simon, 1989) design will be used to test the superiority of the combination

of neoadjuvant therapy with Ampley monoclonal antibody as compared with the historical control. The expected Class I error rate for the project (ineffective study drug but effective promotion) $\alpha=0.05$, with 80% confidence. An interim efficacy and safety analysis will be performed when 18 subjects are enrolled. Of the 18 subjects in the first phase, the second phase was not performed if < 2 effective cases of complete pathological response were achieved. If there were ≥ 2 valid cases in Phase 1, continue with Phase 2 until there are a total of 43 subjects. If the total effective cases in the first and second stages were not less than 7, it could be determined that the pCR of the new adjuvant therapy in this study was significantly improved compared with the historical control, thereby demonstrating the superiority and efficacy of the new adjuvant therapy in this study. A 10% dropout rate was considered for this study, which required the recruitment of a total of 48 subjects. The statistical design was calculated using an online statistical tool approved by the Design Department of Sun Yat-sen Memorial Hospital, Sun Yat-sen University (<http://cancer.unc.edu/biostatistics/program/ivanova/simonstwostageDesign.aspx>) (Ivanova & Deal, 2016).

5.4.2 data analysis set

Safety analysis set: Includes all patients who received at least 1 dose of any study drug (any component of neoadjuvant combination therapy).

Efficacy analysis set: Includes all patients who received at least 1 dose of any study drug treatment (any component of neoadjuvant combination therapy) followed by radical cystectomy.

5.6.3 Statistical analysis plan.

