5.4.3 Efficacy analysis

Analysis of primary effectiveness endpoint for 5.4.3.1

The primary endpoint, the pathological complete response rate (pCR rate), was defined as the proportion of patients in the efficacy analysis set who received radical cystectomy after completion of neoadjuvant therapy without residual tumor lesions as assessed by the investigator. Will be analyzed based on the validity analysis set.

5.4.3.2 secondary efficacy endpoint analysis

The pathological descending rate is determined according to the pathological results after surgery to determine whether the disease is descending to below T2. The percentages of CT2N0 → PT0N0, CT3-4AN0 → PT0N0, CT2N0 → \leq PT 1N0, CT3-4AN0 → \leq PT 1N0 were calculated respectively, and the 95% confidence interval (CI) of bilateral Clopper-Pearson for pathological stage reduction rate was calculated, to evaluate the accuracy of the estimate of pathological stage reduction rate. Will be analyzed based on the validity analysis set.

Event-free survival (EFS), is the time from the first neoadjuvant treatment until disease progression, death from any cause, or new onset of other tumors. The Kaplan-Meier(KM) method

will be used to estimate the no-event curve and the corresponding quantiles (including median values). If the two-sided 95% confidence interval for the median can be estimated, the generalized Brookmeyer and Crowley method (Brookmeyer and Crowley, 1982) was used. The KM method will be used to estimate EFS rates at 1 and 2 years from the first dose, and 1 and 2 years after surgery, with the corresponding 95% confidence interval estimated using Greenwood's formula (Greenwood, 1926). The EFS deletion criteria will be in compliance with the FDA Industry Guide: Clinical Trial Endpoints for Approval of Cancer Drugs and Biological Products (FDA 2007). EFS will be analyzed based on the security analysis set.

Overall survival (OS) was defined as the time from the start of treatment to death for any cause. OS will perform similar analyses using the KM method above for populations included in the safety and efficacy analysis sets, respectively. The time curve will be plotted against the KM estimate of OS. The median OS, OS rates 1 and 2 years from the first dose, and OS rates 1 and 2 years after surgery will be calculated and show a bilateral 95% CI.

5.4.4 safety analysis

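### The primary pCR rate leaves out treated patients who never reach cystectomy instead of counting them as non-pCR, and the two-stage rule does not say which patients it counts

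*Protocol*

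**What the plan says.** **The primary denominator.** Protocol section III, item 2.2, sets this condition for entering the effectiveness set: "received at least 1 dose of any study drug treatment (any component of neoadjuvant combination therapy) and had a radical cystectomy following that treatment". Section 5.4.2 repeats this: "Includes all patients who received at least 1 dose of any study drug treatment (any component of neoadjuvant combination therapy) followed by radical cystectomy". Section III, item 3.1, bases the pCR rate (pT0N0) on that set. Section 5.4.3.1 does the same and describes the responders as those "who received radical cystectomy after completion of neoadjuvant therapy without residual tumor lesions as assessed by the investigator".

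**Treated patients without surgery.** Several places foresee them:
- Section 2.1 (background): "some patients lose the opportunity of radical surgery due to adverse events caused by ICIs treatment".
- Section 5.2.4: "Patients who discontinue neoadjuvant therapy early due to disease progression or an intolerable adverse event (AE) before surgery and do not undergo surgery", and separately, "If the investigator determines that physical conditions preclude radical surgery, study treatment will be discontinued".
- Section 5.3.4.2: "If the patient is not suitable for surgery, the investigator decides to give subsequent treatment".
- Section IV, item 1.3 (exit criteria), lists cases where "the operation is not performed although it is assessed by the investigator to be in line with the indications for radical surgery".

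No section counts any of these patients as non-pCR.

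**The decision rule.** Section 5.4.1 sets the interim at 18 enrolled subjects, continues to 43 subjects in total, and recruits 48 to allow for 10% dropout. Section 5.2.6 repeats the 18 subjects. The historical 10% and the expected 25% are given without a denominator.

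**Case-by-case membership.** For patients operated beyond the time limits, section 5.2.4 leaves it to the lead unit to decide whether they enter the analysis.

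**The concern.** Membership of the primary analysis set depends on something that happens after treatment starts and that the treatment can influence. A patient who progresses on the regimen, or whom its toxicity makes unfit for surgery, is a failure of neoadjuvant treatment, yet that patient is removed from the calculation rather than counted against it. For a fixed number of pCRs, the reported rate rises as more patients fail before surgery. That is the wrong direction for the headline result of a regimen meant to bring patients through cystectomy.

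The counting unit matters for a related reason. If the rule counts one group and the reported rate describes another, the same number of pCRs gives two different proportions, and the stated error rates attach to only one of them. The lead unit's discretion adds to this: in an open-label single-arm trial, the decision to include a late-operated patient can be made with that patient's pathology already known.

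**Working it through.** **1. The plan's own design.** Inputs from section 5.4.1: p0 = 0.10, p1 = 0.25, alpha 0.05, 80% power, n1 = 18, n = 43, 10% dropout. An exact binomial search for the Simon optimal design gives n1 = 18 and n = 43, continuing at ≥3/18 and succeeding at ≥8/43, with alpha 0.0480 and power 0.8003. Inflation: 43/0.9 = 47.8, rounded up to 48. The sample sizes reproduce. The printed cut-offs (≥2 and ≥7) are each one lower and give alpha 0.1218 and power 0.9153; that is a separate matter. The illustrations in step 4 use ≥3/18 and ≥8/43 because those match the stated alpha and power.

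**2. Size of the difference in the reported rate.** Let f be the share of treated patients who are operated. All pCRs occur in operated patients, so

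operated-only rate = all-treated rate / f.

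The protocol gives no f, so a range is assumed. The value 0.90 borrows the 10% dropout allowance, which section 5.4.1 does not tie to surgery.

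| f | Reported rate if the all-treated rate is 25% |
|---|---|
| 0.95 | 0.25/0.95 = 26.3% |
| 0.90 | 0.25/0.90 = 27.8% |
| 0.85 | 0.25/0.85 = 29.4% |
| 0.80 | 0.25/0.80 = 31.3% |

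In whole patients, with 48 treated and 12 pCRs, the all-treated rate is 12/48 = 25.0%. With 2, 5 or 10 patients not operated, the reported rate is 12/46 = 26.1%, 12/43 = 27.9% or 12/38 = 31.6%.

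**3. Which patients do the 18 and the 43 count?** Two readings are open.
- *Enrolled or treated subjects.* This fits the interim trigger of 18 enrolled and the plain use of the word subjects.
- *Evaluable, that is operated, patients.* This fits the inflation from 43 to 48, which would otherwise have little purpose.

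The text does not choose.

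**4. What each reading would imply (illustrative).** The exact two-stage binomial probability of success is evaluated at the shifted rate.

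| f | Type I error if the 43 are operated and 10% is an all-treated rate (p = 0.10/f) | Power if the 43 include non-operated and 25% is an operated rate (p = 0.25f) |
|---|---|---|
| 1.00 | 0.048 | 0.800 |
| 0.95 | 0.061 | 0.753 |
| 0.90 | 0.079 | 0.697 |
| 0.85 | 0.101 | 0.634 |
| 0.80 | 0.131 | 0.565 |

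The two columns rest on opposite readings of the 43, so they cannot both apply. If the 43, the 10% and the 25% all refer to operated patients, neither applies.

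**5. Power once the rule is restated for treated patients.** Take 48 treated, f = 0.90, and 25% as an operated rate, so the all-treated alternative is 0.25 × 0.90 = 0.225. With ≥2/18 then ≥9/48, alpha at 0.10 is 0.044 and power at 0.225 is 0.762. With ≥3/18 then ≥9/48, they are 0.036 and 0.693.

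**The case against.** The strongest reply is that the choice is declared and consistent. The primary objective is the pCR rate after radical cystectomy, the efficacy set follows from it, and the study calls itself exploratory. A reader with the number treated and the number of pCRs can recover the all-treated rate. EFS is analysed in all treated patients and OS in both sets (section 5.4.3.2), so failure to reach surgery is not hidden from the whole report. An SAP not seen here could add a supportive all-treated rate.

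Much of this stands. The operated-only rate is a legitimate quantity and should be kept. The reply does not make it the right primary result: the protocol itself fixes that denominator, and the figure improves when patients fail before surgery.

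A reader might go further and infer that the reported rate definitely contradicts the decision rule. The text does not support that. The inflation to 48 makes 43 evaluable patients a natural reading, under which the final count and the rate share a denominator. Only the stage 1 trigger clearly uses another unit, and it may fix no more than the timing of the interim. A reader might also infer that type I error is inflated or power lost as the plan stands. Each needs an assumption about the 43, the 10% and the 25% that the protocol does not state.

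The phrase in section 5.4.3.1 about completing neoadjuvant therapy could be read as excluding operated patients who stopped early. Section 5.2.4 keeps such patients evaluable when they are operated within the time frame, so this is a small wording repair.

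**Conclusion.** The point holds for the denominator. As written, the primary pCR rate excludes treated patients who are not operated, and nothing counts them as non-pCR. The reported rate exceeds the all-treated rate by 1/f as soon as one treated patient is not operated and one pCR occurs. At an assumed f of 0.95 to 0.80, an all-treated 25% is reported as 26.3% to 31.3%. The direction is arithmetic; the size rests on f, which the protocol does not give.

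On the decision rule, the finding is narrower: the counting unit of the 18 and 43, and the denominators of the 10% and 25%, are not stated. The error-rate figures show what is at stake under particular readings and are not demonstrated consequences. This should be corrected, but it does not invalidate the design.

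**What to change.** - Make all patients with at least one dose (the existing safety set) the primary pCR denominator in section III and sections 5.4.2 and 5.4.3.1. Count no cystectomy or no pathology as non-pCR. Report the cystectomy-set rate as supportive.
- Use the same denominator for the stage 1 and final counts in sections 5.2.6 and 5.4.1, and state whether the 10% and the 25% are all-treated or operated rates.
- When the printed cut-offs are corrected, restate cut-offs and power for the number of treated patients.
- Replace the lead unit's case-by-case decision on analysis eligibility in section 5.2.4 with inclusion of all treated patients, and align the completion wording in section 5.4.3.1 with section 5.2.4.

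The cost is a protocol amendment to definitions and counts. The set already exists and no new data are needed. The reported pCR rate will be lower, for example 25.0% instead of 27.8% at 90% operated. If 25% was meant as an operated-only rate, some power is lost. How much depends on the recomputed cut-offs: in the 48-patient example at 90% operated, power is 0.762 with ≥2/18 then ≥9/48. The sponsor should accept or address that loss openly. This point does not by itself require added enrolment.

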5.4.3 Efficacy analysis

Analysis of primary effectiveness endpoint for 5.4.3.1

The primary endpoint, the pathological complete response rate (pCR rate), was defined as the proportion of patients in the efficacy analysis set who received radical cystectomy after completion of neoadjuvant therapy without residual tumor lesions as assessed by the investigator. Will be analyzed based on the validity analysis set.

5.4.3.2 secondary efficacy endpoint analysis

The pathological descending rate is determined according to the pathological results after surgery to determine whether the disease is descending to below T2. The percentages of CT2N0 → PT0N0, CT3-4AN0 → PT0N0, CT2N0 → \leq PT 1N0, CT3-4AN0 → \leq PT 1N0 were calculated respectively, and the 95% confidence interval (CI) of bilateral Clopper-Pearson for pathological stage reduction rate was calculated, to evaluate the accuracy of the estimate of pathological stage reduction rate. Will be analyzed based on the validity analysis set.

Event-free survival (EFS), is the time from the first neoadjuvant treatment until disease progression, death from any cause, or new onset of other tumors. The Kaplan-Meier(KM) method

will be used to estimate the no-event curve and the corresponding quantiles (including median values). If the two-sided 95% confidence interval for the median can be estimated, the generalized Brookmeyer and Crowley method (Brookmeyer and Crowley, 1982) was used. The KM method will be used to estimate EFS rates at 1 and 2 years from the first dose, and 1 and 2 years after surgery, with the corresponding 95% confidence interval estimated using Greenwood's formula (Greenwood, 1926). The EFS deletion criteria will be in compliance with the FDA Industry Guide: Clinical Trial Endpoints for Approval of Cancer Drugs and Biological Products (FDA 2007). EFS will be analyzed based on the security analysis set.

Overall survival (OS) was defined as the time from the start of treatment to death for any cause. OS will perform similar analyses using the KM method above for populations included in the safety and efficacy analysis sets, respectively. The time curve will be plotted against the KM estimate of OS. The median OS, OS rates 1 and 2 years from the first dose, and OS rates 1 and 2 years after surgery will be calculated and show a bilateral 95% CI.

5.4.4 safety analysis

Safety was evaluated by monitoring and documentation of all adverse events classified by NCI-CTCAE v5.0 or Clavien-Dindo. Laboratory values (eg, hematology, clinical biochemistry, urinalysis), vital signs, ECGs, and physical examinations will also be considered in evaluating safety. All safety data in the safety analysis set will be analyzed using descriptive statistics.

The safety analysis set was defined to include all patients who received ≥ 1 dose of neoadjuvant therapy from the study protocol. EFS rate, OS rate, and adverse events of drug exposure (including duration and dose) will be summarized by safety analysis set population. Adverse events will be described coded according to the Medical Dictionary for Regulatory Activities (MedDRA) terms and graded according to NCI-CTCAE v5.0 or Clavien-Dindo.

Adverse events in 5.4.4.1

AE reporting terms (investigator description in eCRF) will be coded using the International Dictionary of Medical Terms (MedDRA). AEs were coded according to low-level terms, preferred terms, and major system organ class in MedDRA (version 20.0 or higher).

Vi. research interventions *

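### OS timed from first dose in the operated-only efficacy set carries guaranteed survival to surgery, and post-surgery EFS and OS rates are assigned to a set that includes unoperated patients

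*Protocol*

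**What the plan says.** Protocol section 5.4.3.2 fixes the OS clock: "Overall survival (OS) was defined as the time from the start of treatment to death for any cause". It then plans Kaplan-Meier analyses of OS "for populations included in the safety and efficacy analysis sets, respectively", and asks for "OS rates 1 and 2 years from the first dose, and OS rates 1 and 2 years after surgery" without tying either kind of rate to one of the two sets.

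For EFS, the same section says that it "is the time from the first neoadjuvant treatment until disease progression, death from any cause, or new onset of other tumors". It asks for "EFS rates at 1 and 2 years from the first dose, and 1 and 2 years after surgery", and closes with "EFS will be analyzed based on the security analysis set" (the safety set, in translation). Section 5.4.4 repeats that EFS and OS rates are summarised in the safety set.

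The two sets are defined in section III (Analysis set) and again in 5.4.2. The safety set "Includes all patients who received at least 1 dose of any study drug"; surgery is not required. The efficacy set needs at least one dose and a radical cystectomy afterwards.

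Section 5.2.4 foresees dosed patients who are never operated, because of progression, an intolerable adverse event or unfitness for surgery. It also says that patients who progress during neoadjuvant treatment but still meet the surgical indication go on to surgery and remain evaluable.

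**The concern.** Membership of the efficacy set depends on an event, cystectomy, that comes weeks to months after the OS clock starts. Two things follow for OS from first dose in that set. Each member contributes a stretch of follow-up during which death was impossible by construction. And dosed patients who died early or never reached surgery are left out, using information not available at time zero. Both push the curve up.

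The study has no concurrent control, and section 2.1 says it is meant to guide a later Phase III trial. An inflated OS curve could therefore be carried into planning or set against historical series that count from treatment start in all patients. Section 5.4.3.2 does not say which of the two OS curves is the reported one.

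The post-surgery rates have the opposite mismatch. The clock starts at surgery, but the stated set includes patients who had none.

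**Working it through.** **No plan figure to reproduce.** The protocol states no expected OS or EFS rate and no expected number of unoperated patients. Only the guaranteed time can be derived from it; the sizes in points rest on assumptions.

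**Step 1: guaranteed survival time.** Inputs: 21-day cycles, at most four (sections 5.2 and 6.1); surgery 28 to 42 days after the last dose (visit schedule, 5.3.5). Nominal days from first dose to surgery = 21 × (cycles − 1) + 28 to 42.

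| Cycles given | Days from first dose to surgery |
|---|---|
| 1 | 28–42 |
| 2 | 49–63 |
| 3 | 70–84 |
| 4 | 91–105 (13–15 weeks) |

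Section III starts OS and EFS at enrollment rather than first treatment. That is a separate inconsistency; an earlier clock could only lengthen these intervals.

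**Step 2: effect of guaranteed time alone (illustration).** Assume exponential survival with 1-year OS equal to S1, and that everyone alive at time s is operated. All dosed: S(t) = S1^t. Operated only: S(t)/S(s) = S1^(t − s). With s = 91/365.25 = 0.249 or 105/365.25 = 0.287 years, and S1 = 0.90 for example, the operated-only 1-year rate is 0.90^0.751 = 92.4%, against 90.0%.

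| Assumed 1-year OS, all dosed | Excess at 1 year (points) | Excess at 2 years (points) |
|---|---|---|
| 95% | 1.2–1.4 | 1.2–1.3 |
| 90% | 2.4–2.8 | 2.2–2.5 |
| 85% | 3.5–4.1 | 3.0–3.5 |
| 80% | 4.6–5.3 | 3.7–4.2 |

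**Step 3: effect when unoperated patients do worse (illustration).** Let a fraction q of dosed patients be unoperated. All-dosed OS = (1 − q) × OS(operated) + q × OS(unoperated), so the gap is q × [OS(operated) − OS(unoperated)]. All inputs are assumed 1-year values.

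| q | OS operated | OS unoperated | OS all dosed | Gap (points) |
|---|---|---|---|---|
| 10% | 90% | 60% | 87.0% | 3.0 |
| 10% | 85% | 50% | 81.5% | 3.5 |
| 10% | 90% | 50% | 86.0% | 4.0 |
| 20% | 90% | 60% | 84.0% | 6.0 |
| 20% | 85% | 50% | 78.0% | 7.0 |
| 20% | 90% | 50% | 82.0% | 8.0 |

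Steps 2 and 3 are alternative illustrations of the same bias and must not be added together.

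**Step 4: post-surgery rates.** With 48 dosed and q of 10 to 20%, 48 × 0.10 = 4.8 and 48 × 0.20 = 9.6, so about 5 to 10 patients in the safety set would have no surgery date and hence no time zero. For EFS there is a second group: operated patients who progressed first, whom 5.2.4 keeps evaluable, have their event before the surgery clock starts. Section 5.4.3.2 states no rule for either group. OS from surgery in the efficacy set, by contrast, is well defined.

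**The case against.** The strongest defence is that sound estimates are already planned. OS is also analysed in the safety set, EFS is assigned only to the safety set, and 5.4.4 names only the safety set when it returns to EFS and OS rates. The efficacy-set curve is an addition, and its distance from the safety-set curve would be visible. This stands, and it limits the harm.

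The word closing "for populations included in the safety and efficacy analysis sets, respectively" could be read as pairing first-dose OS with the safety set and post-surgery OS with the efficacy set, which would remove the guaranteed time. The text does not state that pairing: OS has a single definition, from the start of treatment, and the rates are listed without allocation to a set. The pairing would also leave EFS unrepaired.

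On the post-surgery rates, one can say that they can only concern operated patients and that an analysis plan could name that subset. That is fair as far as it goes. But the protocol does fix a population for EFS, and it is the wrong one for a clock that starts at surgery.

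Finally, OS and EFS are secondary and descriptive, and the continuation and success rules use pCR alone. With 43 patients and 80% survival, the 95% half-width is about 1.96 × √(0.80 × 0.20/43) = 12 points, ignoring censoring, which is larger than any bias shown above. This also stands, but a wide interval does not remove a bias whose direction is known.

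**Conclusion.** The point holds for one planned estimate, OS from first dose in the efficacy set, and in a lesser form for the rates counted from surgery. The guaranteed time follows from the protocol's own schedule. The upward direction needs only some deaths before surgery or worse survival among unoperated patients. The size cannot be found from the documents: about 1 to 5 points at 1 year from guaranteed time alone (assumed 1-year OS 80 to 95%, surgery at 13 to 15 weeks), or about 3 to 8 points with 10 to 20% unoperated and the assumed survival differences. The 10% dropout in 5.4.1 is not described as a non-operation rate, so it does not anchor these figures.

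Four stronger readings are not supported:

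- A reader might infer that all the survival results are biased in this way. Safety-set OS and EFS from first dose are not.
- A reader might infer that every patient who progresses early is removed. Those who are still operated stay in the efficacy set; only the unoperated leave it.
- A reader might infer that post-surgery EFS cannot be computed. It can, in operated patients who are event-free at surgery; what is wrong is the stated population.
- A reader might take any single figure for the bias as established. Every one depends on survival rates that the protocol does not give.

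**What to change.** Amend section 5.4.3.2 as follows:

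- State that OS and EFS from first dose are estimated in the safety (all-treated) set and that these are the reported estimates.
- State that the 1- and 2-year post-surgery rates are estimated only in operated patients, with time zero at surgery and, for EFS, only in those event-free at surgery. Label them as conditional on reaching surgery.
- Drop OS from first dose in the efficacy set, or replace it with OS from surgery.

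The matching sentence in 5.4.4 should be aligned. The cost is a few sentences and no new data. One descriptive curve is lost, and the reported OS may look slightly less favourable.
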